4.2 Exclusion Criteria

Individuals who meet any of these criteria are not eligible for enrollment as study participants:

- History of severe anaphylaxis as defined by hypoxia (cyanosis or SpO2 <92% during reaction), documented
 hypotension (documented systolic BP >30% below predicted normal for sex, height, weight or from known
 baseline), neurological compromise (confusion, loss of consciousness), or incontinence.
- Severe or Moderate asthma as defined using the severity criteria of the current NHBLI Guidelines for the Diagnosis and Management of Asthma (http://www.nhlbi.nih.gov/guidelines/asthma/).

- Poorly-controlled asthma as defined by FEV1 <80% or any of the following symptoms: nighttime awakening >2 days/week or rescue medication use >2 days / week.
- Diagnosis of other severe or complicating medical problems, including autoimmune or chronic immune inflammatory conditions or gastrointestinal inflammatory conditions, including Celiac Disease, Inflammatory Bowel Disease and Eosinophilic Gastrointestinal Disorders
- Inability to cooperate with and/or perform oral food challenge procedures.
- Primary Immune Deficiency
- Allergy to oat confirmed by skin prick testing and history
- Current use of beta blockers, angiotensin converting enzyme inhibitors, or monoamine oxidase inhibitors
- Women of childbearing potential who are pregnant, planning to become pregnant, or breastfeeding
- Hematocrit < 0.36 for adult females or < 0.38 for adult males
- Weight <23 kg
- Use within the past 6 months of other systemic immunomodulatory treatments including allergen immunotherapy, or use of biologics with an immune target, including omalizumab.
- Past or current medical problems or findings from physical examination or laboratory testing that are not listed above, which, in the opinion of the investigator, may pose additional risks from participation in the study, may interfere with the participant's ability to comply with study requirements or that may impact the quality or interpretation of the data obtained from the study may also exclude a participant from the study.

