If the participant has a Build Up dose in the MGH CRC and experiences symptoms that require treatment in accordance with Figure 15.4, the patient will continue on the previously tolerated dose for the next two week interval.

Participants may also develop symptoms during the subsequent at home administrations of the Build Up doses. The participants will be instructed to contact study staff for any symptoms. The study physician's judgment will be required to determine the best course of action with possible actions being the following:

- 1. Continue with daily home dosing at the current Build Up dose
- 2. Continue with daily home dosing at the previously tolerated daily dose for the next (additional) 2-week interval
- 3. Return the following day to the MGH CRC for repeat trial at the current Build Up dose
- 4. Return the following day to the MGH CRC for dosing at a previously tolerated dose
- 5. Discontinue dosing

For reactions for which epinephrine was given (1-2 doses) or was indicated (as outlined in Figure 15.4), treatment will be withheld until it can be resumed (as below) in the MGH CRC. As per individual stopping rules (see section 8.1.2) participants who receive more than two doses of epinephrine for a single reaction will be withdrawn. For minor reactions (appropriately treated without epinephrine as outlined in Figure 15.4), treatment will be resumed at home unless the study physician determines that resumption should take place in the CRC.

Resumption of treatment will proceed as follows: 50% of the previously tolerated amount for 4-5 days, 75% for 4-5 days and then 100%. The previously scheduled Build Up visit will be postponed to take place 2 weeks (12 days minimum) after resumption of the 100% dose.

If a participant fails to tolerate 3 consecutive Build Up attempts prior to reaching 600 mg or if the participant fails to reach 600 mg by week 50, then the participant will be considered a treatment failure.

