If the participant misses one or two days of the daily dose for any reason then he or she will continue on the same dose. If the participant misses the dose for three days, the participant will be asked to return to the MGH CRC for the next daily dose to ensure that there are no adverse effects from resuming dosing. If the participant misses their dose for four or more days, he/she will have to return to the MGH CRC for a modified rush protocol to escalate back to the highest previously tolerated dose beginning at 50%. For the duration of the study, the participant will be asked to continue to follow a peanut elimination diet.

7.7.2.3 Maintenance At the end of the Build Up phase, the participants will continue on the achieved daily dose for 12 weeks in the maintenance phase. Participants in a reported study have tolerated a very similar dosing schedule with minimal symptoms [?]. Participants will enter the Maintenance phase at the highest dose tolerated by week 50 (at least 600 mg).

Participants may develop symptoms during the at home administrations of the Maintenance doses. The participants will be instructed to contact study staff for any symptoms. The study physician's judgment will be required to determine the best course of action with possible actions being the following:

- 1. Continue with daily home dosing at the current Maintenance dose
- 2. Continue with daily home dosing at 50% of the Maintenance dose
- 3. Return the following day to the MGH CRC for observed trial at the current Maintenance dose
- 4. Return the following day to the MGH CRC for observed trial of a reduced dose (e.g. 50%, 75%)
- 5. Discontinue dosing

For reactions for which epinephrine was given (1-2 doses) or was indicated (as outlined in Figure 15.4), treatment will be withheld until it can be resumed (as below) in the MGH CRC. As per individual stopping rules (see section 8.1.2) participants who receive more than two doses of epinephrine for a single reaction will be withdrawn. For minor reactions (appropriately treated without epinephrine as outlined in Figure 15.4), treatment will be resumed at home unless the study physician determines that resumption should take place in the CRC.

Resumption of treatment will proceed as follows: 50% of the previously tolerated amount for 4-5 days, 75% for 4-5 days and then 100%. The previously scheduled Build Up visit will be postponed to take place 2 weeks (12 days minimum) after resumption of the 100% dose.

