8.1.2 Individual Stopping Rules

Safety of the participant will remain of primary importance. Any participant who develops severe systemic anaphylaxis, defined by any of the following: hypoxia (cyanosis or SpO2 <92% during reaction), documented hypotension (systolic BP>30% fall from baseline systolic BP), neurological compromise (confusion, loss of consciousness), or incontinence after ingestion of peanut, significant hypotension during any stage of the protocol, and/or requires more than 2 injections of epinephrine during any administration of the peanut product will be withdrawn from the study.

Participants who are ingesting daily maintenance dose of peanut will be dropped from the study if they are having NCI-CTCAE grade 2 or higher gastrointestinal, respiratory, or dermatologic symptoms at home within 2 hours of taking the daily dose of peanut for 5 or more consecutive days. The determination of symptoms and their relativity to the daily dose rather than a concurrent illness must be evaluated by the PI and thought to be related to the peanut before being dropped from the study. Recurrent symptoms for 5 or more consecutive days that are occurring more than 2 hours after the daily IT dose may prompt an individual being dropped, if the investigator believes that they are related to IT dosing.

Mild or moderate adverse events such as nausea, vomiting, increased asthma symptoms, allergic dermal reactions, or fever will cause the procedure on the individual patient to be discontinued, will be reported in the required timely manner to the Partners IRB, but will not automatically cause the study to be halted. Each participant will be treated

for worsening asthma, atopic dermatitis, or suspected EoE symptoms and removed from the study when deemed necessary by the PI.

8.1.3 Early Discontinuation of Investigational Product(s) / Intervention(s) with continued study participation / follow-up

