At home reactions are anticipated and from previous reports, co-factors of intercurrent illness and exercise have been identified. All participants will have epinephrine auto-injectors and diphenhydramine and will be instructed to have them available at all times and trained in their use (i.e. an emergency action plan) as indicated in Section 15.5 and as is clinically indicated generally for all individuals with a diagnosis of immediate-type food allergies. If reactions occur in association with at home doses, they will be instructed to treat according to the action plan and contact study staff.

Any reaction for which epinephrine was given or was indicated by signs/symptoms defined in Figure 15.4 will be immediately reported to the study nurse or physician. Reactions for which epinephrine was given (1-2 doses) or was indicated (as outlined in Figure 15.4), treatment will be withheld until it can be resumed (as below) in the MGH CRC. As per individual stopping rules (see section 8.1.2) participants who receive more than two doses of epinephrine for a single reaction will be withdrawn. For minor reactions (appropriately treated without epinephrine as outlined in Figure 15.4), treatment will be resumed (as described in Section 7.7.2.2) at home unless the study physician determines that resumption should take place in the CRC.

Resumption of treatment will proceed as follows: 50% of the previously tolerated amount for 4-5 days, 75% for 4-5 days and then 100%. The previously scheduled Build Up visit will be postponed to take place 2 weeks (12 days minimum) after resumption of the 100% dose.

The same protocol will be recommended when signs/symptoms of acute respiratory or gastrointestinal infection occur. An adverse event will be followed until any of the following takes place: a) it is resolved, b) participant is stable, c) a minimum of 30 days after participant is terminated from the study and the Independent Safety Monitor and the Principal Investigator determine that follow-up is complete. An abnormal value or result from a clinical or laboratory evaluation (e.g., a radiograph, an ultrasound, or an electrocardiogram) can also indicate an adverse event. If this is the case, then the evaluation that produced the value or result should be repeated until the value

AADCRC Protocol 2012P002153

38 of 68

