15.4 Treatment Table

Signs / Symptoms	Treatments
LUNG: wheeze, cough	 Epinephrine, IM; auto-injector or 1:1,000 solution IM (anterior-lateral thigh) 0.3 mg epinephrine autoinjector, IM (anterior-lateral thigh) OR Epinephrine (1:1,000 solution) (IM), 0.01 mg/kg per dose; maximum dose, 0.5 mg per dose (anterior-lateral thigh) H1 antihistamine: diphenhydramine 1 to 2 mg/kg per dose Maximum dose, 50 mg IV or oral (oral liquid is more readily absorbed than tablets) Bronchodilator (b2-agonist): albuterol MDI (child: 4-8 puffs; adult: 8 puffs) or
	 Nebulized solution (child: 1.5 ml; adult: 3 ml) every 20 minutes or continuously as needed 4. Supplemental oxygen therapy 5. Corticosteroids Prednisone at 1 mg/kg with a maximum dose of 60 to 80 mg oral or Methylprednisolone at 1 mg/kg with a maximum dose of 60 to 80 mg IV
HEART: hypotension, cardiovascular collapse	 Epinephrine, IM; auto-injector or 1:1,000 solution Same as above H1 antihistamine: diphenhydramine Same as above Corticosteroids Same as above H2 antihistamine: ranitidine 1 to 2 mg/kg per dose Maximum dose, 75 to 150 mg oral or IV Vasopressors (other than epinephrine) for refectory hypotension, titrate to effect Glucagon for refractory hypotension, titrate to effect Child: 20-30 mg/kg Adult: 1-5 mg Dose may be repeated or followed by infusion of 5-15 mg/min Atropine for bradycardia, titrate to effect IV fluids in large volumes if patient presents with orthostasis, hypotension, or incomplete response to IM epinephrine Place the patient in recumbent position if tolerated, with the lower extremities elevated

Signs / Symptoms	Treatments
THROAT: hoarse, swelling	 Epinephrine, IM; auto-injector or 1:1,000 solution Same as above H1 antihistamine: diphenhydramine Same as above Corticosteroids Same as above Consider H2 antihistamine: ranitidine Same as above
SKIN: hives, swelling, pruritus	 H1 antihistamine: diphenhydramine Same as above Consider Epinephrine, IM; auto-injector or 1:1,000 solution Same as above Consider H2 antihistamine: ranitidine Same as above
GUT: vomiting, nausea, diarrhea, pain or discomfort	 H1 antihistamine: diphenhydramine Same as above Consider Epinephrine, IM; auto-injector or 1:1,000 solution Same as above Consider H2 antihistamine: ranitidine Same as above
MOUTH: hives, swelling, oral pruritus	 H1 antihistamine: diphenhydramine Same as above Consider Epinephrine, IM; auto-injector or 1:1,000 solution Same as above Consider H2 antihistamine: ranitidine Same as above

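### The dosing sections restate only the epinephrine-count ground of stopping rule 8.1.2, so they diverge from it for severe anaphylaxis treated with two or fewer epinephrine doses

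*Combined protocol and SAP*

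**What the plan says.** **The stopping rule.** Section 8.1.2 begins: "Any participant who develops severe systemic anaphylaxis, defined by any of the following: hypoxia (cyanosis or SpO2 <92% during reaction". It goes on to documented hypotension, neurological compromise and incontinence after peanut ingestion. Joined by and/or is a separate ground, that the participant "requires more than 2 injections of epinephrine during any administration of the peanut product will be withdrawn from the study". Section 4.3 lists meeting any individual stopping rule among the reasons for early termination.

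**The dosing sections.** Section 7.7.2.2 (Build Up) covers reactions for which "epinephrine was given (1-2 doses) or was indicated (as outlined in Figure 15.4), treatment will be withheld until it can be resumed" in the research unit, by steps of 50%, 75% and 100%. Its next sentence reads: "As per individual stopping rules (see section 8.1.2) participants who receive more than two doses of epinephrine for a single reaction will be withdrawn". Section 7.7.2.3 (Maintenance) uses the same wording. Section 8.2.2.4 repeats it: "Reactions for which epinephrine was given (1-2 doses) or was indicated (as outlined in Figure 15.4), treatment will be withheld until it can be resumed", again followed by the more-than-two-doses ground alone.

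**In-clinic Build Up doses.** A separate sentence in 7.7.2.2 says that after symptoms needing Figure 15.4 treatment, the patient stays on the dose tolerated before for the next two weeks. It does not refer to 8.1.2.

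**The treatment table.** Figure 15.4 has a row "HEART: hypotension, cardiovascular collapse", with epinephrine as the first treatment listed.

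**The concern.** The dosing sections sort reactions by epinephrine alone: minor reactions treated without it, reactions with one or two doses given or epinephrine indicated, and reactions with more than two doses. Section 8.1.2 sorts by severity as well. A severe reaction treated with two or fewer doses has no category of its own in the dosing sections. On their wording it falls in the resumption group, while 8.1.2 withdraws the participant.

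Three things are at stake.

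- **Safety.** The divergence concerns re-exposure to peanut after the kind of reaction that 8.1.2 defines as severe. More than one such event suspends enrolment under 8.1.1, and a participant who resumed could supply a further one.
- **Conduct.** Section 8.3.1.2 gives, as an example of a major deviation, a participant who met withdrawal criteria and stayed in the study. Staff could reach that position by following the dosing text.
- **Analysis.** The per protocol set is the active participants who complete DBPCFC3 (9.2.2). A withdrawn participant cannot enter it; one who resumes may.

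**Working it through.** No arithmetic applies, and the plan gives no figure to reproduce. The check compares what each text does with a Build Up or Maintenance reaction, using only the two 8.1.2 grounds in question: severe anaphylaxis and more than two injections.

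| Reaction | Sections 7.7.2.2, 7.7.2.3, 8.2.2.4 | Section 8.1.2 | Result |
|---|---|---|---|
| Severe, more than 2 doses | Withdraw | Withdraw, on both grounds | Agree |
| Not severe, more than 2 doses | Withdraw | Withdraw, on the injection count | Agree |
| Not severe, 1-2 doses | Hold, then resume | Neither ground met | Agree |
| Severe, 1-2 doses | Within the resumption wording | Withdraw, on severity | Diverge |
| Severe, 0 doses, epinephrine indicated per Figure 15.4 | Within the resumption wording | Withdraw, on severity | Diverge |

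**Does the severity ground depend on the epinephrine count?** No. It is joined to the injection count by and/or. Section 8.1.1 likewise lists severe systemic anaphylaxis and repeated epinephrine as separate triggers at study level.

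**Can a severe reaction involve two or fewer doses?** The plan allows for it. The heart row of Figure 15.4 lists other vasopressors, glucagon and intravenous fluids besides epinephrine, so the number of epinephrine doses does not stand in for severity.

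**How far does the zero-dose row reach?** It holds only where epinephrine was indicated under Figure 15.4. The figure names hypotension and cardiovascular collapse. It does not name hypoxia, neurological compromise or incontinence, so a zero-dose reaction with one of these enters only through another listed sign.

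**The in-clinic sentence.** It covers any symptom needing Figure 15.4 treatment, which includes the heart row. It states what will happen to the dose and makes no exception for 8.1.2. This is the plainest instance of the divergence.

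**Effect on the analysis.** The plan randomises 30 participants to active treatment and anticipates 22 completing DBPCFC3. It gives no rate of severe anaphylaxis during Build Up or Maintenance, so the expected number affected, and any shift in the primary comparison, cannot be calculated.

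**The case against.** The strongest reply is that the sections can be read together. Section 8.1.2 is categorical, 4.3 takes in the stopping rules, and each resumption paragraph cites 8.1.2 in its next sentence. On that reading the stopping rule applies first, and resumption concerns only those still in the study. Other controls point the same way: reactions where epinephrine was given or indicated are reported at once to the study nurse or physician, and serious events reach the medical officer and the safety monitor within 24 hours (8.2.4.1). A severe event needing an emergency room visit or hospitalisation suspends study procedures (8.1.1).

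This makes an unnoticed restart less likely, but it does not remove the divergence. The cross-reference tells the reader what 8.1.2 says and omits the severity ground. No section states which text prevails. Section 4.3 says participants may be terminated, which is weaker than 8.1.2. The in-clinic sentence has no cross-reference at all, and a reaction managed within the research unit need not meet the 8.1.1 trigger.

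A reader might infer more than the text supports:

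- **That the protocol restarts and withdraws the same person, or orders a restart after any reaction treated with one or two doses.** It does not. The resumption wording is conditional, and stopping dosing is a listed option left to the physician's judgment in both dosing sections.
- **That every severe reaction with two or fewer doses is affected.** Figure 15.4 limits the zero-dose cases, and food challenges and the Modified Rush have their own text.
- **That each affected participant is one of the 22.** That does not follow; such a participant need not have been among those who would complete.
- **That the entry exclusion in 4.2 for "History of severe anaphylaxis as defined by hypoxia (cyanosis or SpO2 <92% during reaction" and similar signs adds a further contradiction.** An entry criterion does not conflict with an on-study rule, and 4.2 measures hypotension against predicted normal or known baseline, whereas 8.1.2 uses a fall from baseline.

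**Conclusion.** The point holds as an internal inconsistency in a participant-safety rule. Three sections restate 8.1.2 incompletely, and one sentence in 7.7.2.2 omits it. The texts diverge for Build Up and Maintenance reactions that meet the 8.1.2 severe definition with one or two epinephrine doses, or with none where epinephrine was indicated under Figure 15.4. The in-clinic sentence extends this to any severe Build Up reaction that needs Figure 15.4 treatment and was given no more than two doses. Elsewhere the two grounds and the dosing text agree.

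The conclusion rests on the wording alone, and on reading and/or in 8.1.2 as making severity sufficient by itself. The effect on the per protocol set is real in direction, since the rule affects who can complete DBPCFC3, but its size is unknown. This review takes no view on which clinical rule is right.

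**What to change.** Reconcile 7.7.2.2 (including its in-clinic Build Up sentence), 7.7.2.3 and 8.2.2.4 with 8.1.2:

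1. State which rule governs a reaction that meets the 8.1.2 severe definition with two or fewer epinephrine doses. The sponsor and clinicians decide this.
2. Wherever 8.1.2 is cited, give its complete list of grounds, or refer to it without restating part of it.
3. Make the scope of the resumption paragraph and of the in-clinic sentence match that decision, and say which section prevails if they differ.

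The cost is wording in a protocol amendment. No extra participants, visits or procedures are needed.

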7.7.3 Pulmonary Function Testing

Spirometry is a standard technique performed in our pulmonary function laboratory. In the procedure the participant is asked to take a deep breath to full lung capacity, exhale forcibly and fully, and then inhale fully while breathing

31 of 68

into a tube connected to a spirometry device. The participant is asked to do this 3 times over a 10 minute period. The participant wears a nose clip during the procedure. Spirometry will be performed before and 15 minutes following administration of 2 puffs of albuterol MDI

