6.4 Prohibited Medications

Use within the past year of other systemic immunomodulatory treatment. including allergen immunotherapy, use of biologics with an immune target, including Xolair is prohibited.

Prior to the food challenges, patients will be asked to restrict the use of antihistamines (short-acting, 72 hours: long-acting, 7 days), beta-agonists (12 hours), theophylline (12 hours), and cromolyn (12 hours). For visits that include skin prick testing, patients will be asked to restrict the use of antihistamines (short-acting, 72 hours: long-acting, 7 days).

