7.4 Main Study Visits

7.4.1 Double-Blind Placebo-Controlled Food Challenge 1 (Day 28)

Participants will come to the MGH CRC four weeks (± 4 days) after the baseline visit for a double-blind, placebo -controlled food challenge (DBPCFC1) to peanut. In a DBPCFC, two challenges, one containing placebo material (toasted oat flour) and one containing peanut flour will be performed on two days within a two week period. The order of challenge will be determined by coin toss by the dietitian and will be unknown to the study nurse, investigator, and study participant. The MGH CRC dietician will prepare the challenge materials. Details of the DBPCFC procedure are below in section 7.7.1.

Prior to each challenge, the participant will have a physical exam with vital signs, spirometry, and an IV will be placed. A negative urine pregnancy test will be documented for female participants of child-bearing potential; if the test is positive, the visit will be cancelled and if pregnancy is confirmed, the subject will be withdrawn from the study. The participant will be required to have a baseline FVC and FEV1 >80% of their predicted values and an FEV1/FVC of >0.7 or the DBPCFC will be rescheduled. A study nurse who is blinded to the testing material will administer the challenge. The supervising physician will be present during the challenge and will also be blinded to testing material.

A member of the study staff will follow up with participant with a telephone call the day after the DBPCFC for active safety monitoring.

If the participant reacts at the 300 mg dose of peanut protein or less (443 mg cumulative), he/she will be randomized to receive active or placebo OIT.

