7.4.7 Double-Blind Placebo-Controlled Food Challenge 3 (Day 518)

After 12 weeks of complete peanut avoidance after the DBPCFC2, participants will come to MGH CRC for their third double-blind, placebo-controlled food challenge (DBPCFC3). The DBPCFC3 will be similar to DBPCFC2, differing only in the dosing schedule. See Section 7.7.1 for details.

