7.7 Study Procedures

7.7.1 Double-Blind Placebo-Controlled Food Challenge

In a DBPCFC, two challenges, one containing placebo oat flour and one containing peanut flour, will be performed. The dietitian will perform the preparation of the challenge materials. Prior to the food challenge, participants will be asked to restrict the use of antihistamines (short-acting, 72 hours: long-acting, 7 days), beta-agonists (12 hours), theophylline (12 hours), and cromolyn (12 hours). For DBPCFC1, one challenge will consist of 5 doses of peanut powder given every 20 minutes in increasing amounts up to a cumulative total of 443 mg of peanut protein masked by inclusion in vehicle food. Available vehicle foods will include rice milk, soymilk, mint chocolate mousse, or applesauce. The other challenge will consist of oat flour given also in 5 doses in an identical volume of vehicle food. For the active challenge, the first ingested dose will be 3 mg, then increasing to 10 mg, 30 mg, 100 mg, and 300 mg of peanut protein[?]. The placebo challenge doses will be the equivalent amount of oat flour by weight.

The protocol of the DBPCFC2 will be identical to DBPCFC1, but with additional doses of 1000 mg and 3000 mg for a cumulative dose of 4443 mg peanut protein. DBPCFC3 will follow a slightly different schedule of doses: 30 mg, 100 mg, 300 mg, 1000 mg, and 3000 mg for a cumulative dose of 4430 mg peanut protein.

If the participant has a subjective reaction to one of the doses, the study nurse may repeat that dose or consult with the supervising physician. If symptoms do not recur, the study nurse will continue the DBPCFC protocol after confirming with the supervising physician. If the study nurse is unsure about how to proceed, the supervising physician will be consulted to determine the appropriate action. Food challenges will be immediately stopped and the participant promptly treated for objective signs and symptoms as indicated in Figure 15.4, consistent with the 2010 NIAID-sponsored expert guidelines for the diagnosis and management of food allergies [?].

After the final dose of each challenge or the resolution of any suspected reaction symptoms, the participant will be observed for a minimum of 2 additional hours.

All food challenges will be performed under direct physician supervision. The supervising physician may stop a challenge if he/she feels it is in the best interest of the participant. Incomplete or indeterminate challenges will be rescheduled.

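### Section 7.7.3 ties albuterol to spirometry without naming a visit, so read literally a beta-agonist is given shortly before every food challenge

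*Combined protocol and SAP*

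**What the plan says.** Section 7.7.3 describes the spirometry manoeuvre and ends: "Spirometry will be performed before and 15 minutes following administration of 2 puffs of albuterol MDI". It names no visit and exempts none. No other section describes the procedure.

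Section 7.4.1, on DBPCFC1, says: "Prior to each challenge, the participant will have a physical exam with vital signs, spirometry, and an IV will be placed". The two challenges, one peanut and one placebo, "will be performed on two days within a two week period". The challenge is rescheduled unless baseline FVC and FEV1 exceed 80% of predicted and FEV1/FVC exceeds 0.7. Whether those values are pre- or post-bronchodilator is not stated.

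The same procedure carries forward. Section 7.7.1 says "The protocol of the DBPCFC2 will be identical to DBPCFC1", with two doses added, and section 7.4.7 says "The DBPCFC3 will be similar to DBPCFC2, differing only in the dosing schedule". The Schedule of Events (16.1) has one Pulmonary Function Testing row, marked at every visit, including all three DBPCFCs.

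On medication, section 6.4 says "Prior to the food challenges, patients will be asked to restrict the use of antihistamines" and goes on to beta-agonists. Section 7.7.1 repeats the list, including "beta-agonists (12 hours), theophylline (12 hours), and cromolyn (12 hours". The treatment table (15.4) classes albuterol as a beta-2 agonist and lists it as a treatment for the lung signs, wheeze and cough.

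**The concern.** Participants are asked to arrive free of beta-agonists for 12 hours, and the only spirometry procedure then has staff give them one. The plan does not state why it wants the washout, but avoiding masked reactions is the natural reason.

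Under 7.7.1, objective signs in the treatment table stop a challenge. Wheeze and cough are among them, and albuterol is a listed treatment for both. A masked sign means the challenge continues and the recorded eliciting dose (ED) rises. The ED decides eligibility at DBPCFC1 (reaction at 443 mg or less), failure at DBPCFC2 (below 1443 mg) and the outcome group at DBPCFC3. Those groups define the primary comparison of induced Treg change, planned in section 9.1 as 8 tolerant or partially tolerant participants against 14 failures. Albuterol would reach the Treg endpoint only through group assignment.

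**Working it through.** No figure in the plan needs reproducing. The check sets the sections side by side, then counts the exposure and traces a shifted ED through the group rules.

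**Does the text lead to albuterol before a challenge?**
- 7.4.1 requires spirometry before each challenge.
- 7.7.3 is the only procedure for it and includes albuterol.
- 7.7.1 and 7.4.7 carry this to DBPCFC2 and DBPCFC3, and the schedule agrees.
- Nothing limits the albuterol step or makes challenge-day spirometry pre-bronchodilator only.

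So, read literally, yes.

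**Exposure.** Each DBPCFC takes 2 days.
- Completing all three: 3 × 2 = 6 challenge days, 3 of them peanut days.
- Stopping after DBPCFC2: 2 × 2 = 4 days.

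**Timing.** Inputs are the 15-minute wait (7.7.3), the dose spacing in 7.7.1 ("5 doses of peanut powder given every 20 minutes"), 5 doses at DBPCFC1 and DBPCFC3, 7 at DBPCFC2, and at least 2 hours of observation. The 20-minute interval is stated for DBPCFC1, carried to DBPCFC2 by 7.7.1 and assumed for DBPCFC3. Dosing is assumed to start right after the post-albuterol reading, with no repeated doses.

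Minutes from albuterol to last dose = 15 + (doses − 1) × 20.

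| Challenge | Last dose | End of 2-hour observation |
|---|---|---|
| DBPCFC1, DBPCFC3 | 15 + 4 × 20 = 95 min | 95 + 120 = 215 min |
| DBPCFC2 | 15 + 6 × 20 = 135 min | 135 + 120 = 255 min |

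The washout is 12 × 60 = 720 min. Even at DBPCFC2, dosing would have to start 720 − 135 = 585 min later than assumed before the last dose fell outside it.

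**What a one-step rise in ED can do.** EDs are read as cumulative doses, as the 443, 1443, 430 and 4430 mg thresholds imply:
- DBPCFC1: 3, 13, 43, 143, 443 mg.
- DBPCFC2: the same, then 1443, 4443 mg.
- DBPCFC3: 30, 130, 430, 1430, 4430 mg.

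Using the definitions in 9.2.4.1.1:
- *DBPCFC3, with a DBPCFC1 ED of 13 mg.* At 130 mg the participant is below 430 mg: Treatment Failure. At 430 mg the ratio is 430/13 = 33.1, above 10, and 430 is below 4430: Partial Tolerance.
- *DBPCFC2.* At 443 mg the participant is below 1443 mg: Treatment Failure. At 1443 mg that criterion is no longer met.

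Section 3.1.1 prints the DBPCFC3 failure boundary as 443 mg, under which an ED of 430 mg would meet both definitions. The example therefore follows 9.2.4.1.1. Both cases show what a shift could do. They do not estimate how often it would happen.

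**The case against.** The strongest reply is that the albuterol step was meant for Screening and Baseline only, and the wording gives this real support. Sections 7.2 and 7.3 speak of pulmonary function testing, which is the title of 7.7.3, whereas 7.4.1 and the later visit sections say spirometry. Section 7.7.3 places the technique in a pulmonary function laboratory, while challenges are run at the clinical research center. The gate in 7.4.1 refers to baseline values, which suggests a pre-bronchodilator reading. Elsewhere albuterol appears as rescue or reaction treatment. The literal reading would also put albuterol at every Build Up, Maintenance and Avoidance visit, which seems unlikely to be intended, and a challenge-specific washout could be taken to override a general technique paragraph. The key sentence also ends without a full stop, so a lost qualifier cannot be ruled out, although none is visible.

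This makes the narrower intent plausible but does not put it in the plan. Section 7.7.3 itself uses the word spirometry, and the schedule uses one row for all visits.

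A reply on consequence also stands. Moderate, severe and poorly controlled asthma are excluded, the FEV1 gate applies, and signs in other organs still stop a challenge. The ED moves only if a lower-airway sign would have come first.

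A reader might go further and infer that a one-step rise at DBPCFC1 turns Partial Tolerance into Treatment Failure, for example 13 to 43 mg with a DBPCFC3 ED of 430 mg. The documents do not support that. The ratio is 430/43 = 10.0, and 9.2.4.1.1 requires more than 10-fold for Partial Tolerance and less than 10-fold for failure. Exactly 10-fold is left unclassified.

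**Conclusion.** The point holds as a gap in the wording, at low severity. Followed literally, 7.7.3 puts a beta-agonist inside the plan's own 12-hour window on up to 6 challenge days per completer. That could raise an ED and move a participant across a group boundary. The conclusion assumes that staff apply 7.7.3 as printed. The 95- to 255-minute timings further assume that dosing follows the second reading at once.

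Three stronger readings are not supported. First, the plan does not literally contradict itself: the washout asks participants to restrict their own use, and only its beta-agonist part is touched. Second, the documents do not show that albuterol before challenges was intended. Third, they do not show that the Treg comparison is biased or loses power: the frequency, size and net direction of any misclassification cannot be derived from them.

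**What to change.** In 7.7.3, limit the albuterol step to Screening and/or Baseline. State that challenge-day spirometry is pre-bronchodilator only and that the gate (FVC and FEV1 above 80% of predicted, FEV1/FVC above 0.7) is judged on that reading.

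This costs one or two sentences and adds no visits, tests or participants. The downside is that no reversibility data are collected on challenge days, and no endpoint uses them. If the narrower intent was always meant, the edit simply records it.
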